## 7.4 Immunogenicity: Anti-SYN023 Antibodies

All immunogenicity analyses will be based on subjects who received at least one dose of Study Drug. Immunogenicity will be summarized for all time points as collected and as available. No imputation for missing data will be performed. Data will be transformed as appropriate prior to analysis. The development of anti-SYN023 antibodies will be analyzed on a continuous scale as a categorical variable by treatment assignment, with descriptive statistics.

## **7.5 Pharmacokinetic Analyses**

All PK analyses of serum SYN023 concentrations will be based on subjects who received study drug. Individual analyses will be performed and descriptive statistics will be used to describe the results of individual analyses. PK parameters for SYN023 mAb will be estimated using non-compartmental analysis.  $C_{max}$ ,  $T_{max}$ ,  $AUC_{0-last}$ ,  $AUC_{0-inf}$ ,  $t_{1/2}$ ,  $Cl_p$ , and  $\lambda_z$  will be calculated when possible. Anti-SYN023 antibodies (i.e., anti-CTB011 and anti-CTB012 antibodies) will be determined on Study Day 0 and Study Day 7 through 112, or for subjects who leave the study prior to Day 112, the last blood specimen available.

## **7.6 Safety Analyses**

Safety analyses will be performed using the safety population as defined in Section 7.1. Count (percentage) summaries will be presented by treatment group for all subjects in the safety population.

### **7.6.1 Adverse Events**

The safety profile of SYN023 will be described by treatment group. The primary variable for evaluation of the safety profile will be the number and percentage of unsolicited and solicited adverse events recorded at all available post-vaccination time points. For all presentations of adverse events, additional summaries based on reporting period of adverse events following each study vaccination may also be presented.

The number (percentage) of subjects with adverse events will be summarized by MedDRA system organ class (SOC) and preferred term (PT). Additional summaries will present the number (percentage) of subjects with adverse events by severity and by relationship to study drug; each subject will be counted once per preferred term at the greatest severity or most related state recorded for that term.

Separate summaries of the number (percentage) of subjects with solicited adverse events will also be presented. Solicited adverse events will also be summarized by severity and relationship to study drug; each subject will be counted once per preferred term at the greatest severity or most related state recorded for that term.

In addition, dose-safety curves may be produced to examine the proportion of subjects who experience adverse events by treatment regimen.

Serious adverse events will be recorded through the final study visit for all subjects. Listings will be provided for subjects with serious adverse events.

Listings will be provided for subjects who have discontinued prematurely due to an adverse event.

The number (percentage) of subjects with post-vaccination clinical laboratory values or vital sign values recorded as newly abnormal following study vaccination and meeting toxicity mild

criteria (Grade 1) or above as specified in the Toxicity Table (Appendix E) will be tabulated at each post-vaccination time point and overall. Clinical laboratory and vital sign abnormalities will also be reported as adverse events and will be included in the summary of adverse events.

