### **3.2.4 Exclusion Criteria**

**Subjects must have none of the following at the time of subject ID assignment:**

1. Oral temperature  $\geq 37.5^{\circ}\text{C}$  at screening
2. Complete blood count (CBC) and platelet count abnormal values ( $>5\%$  above the upper limit of normal [ULN] or  $>5\%$  below the lower limit of normal [LLN] per local laboratory parameters) at screening with exception of absolute lymphocyte count.
3. Abnormally elevated aspartate aminotransferase (AST), alanine aminotransferase (ALT), total bilirubin, alkaline phosphatase (ALP), or creatinine (Cr) values at screening (however a single test AST, ALT or ALP may be  $>10\%$  above the ULN per local laboratory parameters)
4. Abnormal PT (INR) PTT
5. Abnormal screening urinalysis result that is, per the investigator, clinically significant, or a screening urine dipstick result of  $\geq 2+$  protein
6. Positive screening urine test for illicit drugs (opiates, cocaine, amphetamines, methamphetamines, barbiturates, benzodiazepines, tetrahydrocannabinol, PCP, MDMA, and methadone)
7. History or evidence of autoimmune disease
8. History or evidence of any past, present, or future possible immunodeficiency state, including laboratory evidence of human immunodeficiency virus (HIV) 1 or 2 infection
9. History or evidence of chronic hepatitis

10. History or evidence of rabies infection
11. History or evidence of any other acute or chronic disease that, in the opinion of the investigator, may interfere with the evaluation of the safety or immunogenicity of the drug or compromise the safety of the subject; for example a clinically relevant history of respiratory, thyroid, gastrointestinal, renal, hepatic, hematological, lymphatic, oncologic, cardiovascular, psychiatric, neurological, musculoskeletal, genitourinary, infective, inflammatory, immunological, dermatological or connective tissue disease
12. History or evidence of allergic disease or reaction, including adverse responses to therapeutic monoclonal antibodies that, in the opinion of the investigator, may compromise the safety of the subject
13. History of non-compliance that, in the opinion of the investigator, will make it unlikely that the subject will comply with the protocol
14. Previous exposure to rabies vaccine
15. Receipt of an immunoglobulin or blood product within 90 days prior to Study Day 0

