### **3.6.3.5 Clinical Assessments and Laboratory Tests**

#### **Abnormal Clinical Assessments and Laboratory Tests**

Results from clinical laboratory tests obtained on the study must be reviewed by the investigator (or a designee who is a medically qualified study team member) within 72 hours of receiving the results to determine if abnormalities exist. If the laboratory value is abnormal and has increased in toxicity grade (see Appendix E for toxicity grading scales) from baseline values, it must be reported as an adverse event and repeated promptly to demonstrate resolution. Additional laboratory tests may be performed if the investigator deems them to be necessary to fully evaluate an adverse event. In the event that the investigator elects to order non-protocol-specified laboratory tests, the investigator must record the rationale for the tests and a determination of clinical significance of the result in the source documents. The investigator must keep the medical monitor informed of adverse events of clinical significance.

Abnormal results and findings will be discussed with the subject, or the subject will be referred for follow-up with their healthcare provider if necessary.

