## **5.3 Definition of Adverse Event**

An adverse event (AE) is defined as any unfavorable or unintended sign, symptom, disease, syndrome, abnormal laboratory finding, or concurrent illness that emerges or worsens after receipt of study drug relative to the subject's pretreatment baseline, whether or not it is considered to be related to the medicinal product.

All conditions that exist prior to administration of the study drug (pre-existing conditions) will be recorded in the subject's medical history to establish baseline. Day-to-day fluctuations in pre-existing conditions that do not represent a clinically significant change in the subject's status will not necessarily be reported as adverse events.

Any adverse change from the subject's baseline condition (determined from screening evaluations conducted to confirm study eligibility) that occurs following the administration of the study drug will be considered an adverse event. This includes the occurrence of a new adverse event or the worsening of a baseline condition, whether or not considered related to the study drug. Intermittent conditions such as headaches in adults or irritability in infants may be present on Study Day 0 but may represent an adverse event if the intensity or duration of the event is worse than usual following receipt of study drug. Adverse events include but are not limited to: adverse changes from baseline that represent increases in toxicity grade according to the Toxicity Table (see protocol appendices), adverse changes in the general condition of the subject, signs and symptoms noted by the subject after study drug administration; concomitant disease with onset or increased severity after study drug administration, and changes in laboratory safety parameters occurring after study drug administration.

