A summary table of shifts from baseline to on-study measurements will be provided. Baseline will be defined in the same manner as described in the preceding paragraph for continuous variables. The shift tables will include normal, low, and high relative to the laboratory reference ranges (or normal-abnormal for categorical variables). Results from repeat tests will not be included in the summary statistics unless the repeat was required (and documented as such) due to technical reasons or an invalid initial result.

If more than one clinical laboratory is used for the study, a formula that takes into consideration the relative normal ranges of each test of laboratories used will be applied in order to normalize these data. The conversion formula used will depend on the typical distribution of the normal range for each laboratory test; the two formulae used are presented below:

- Hemoglobin, hematocrit, and platelet count test results are considered to have a normal distribution ([Chuang-Stein, 1992](#)) and the following formula will be used ([Karvanen J., 2003](#)):

$$s = L_s + (x - L_x) \frac{U_s - L_s}{U_x - L_x}$$

where U= Upper limit; L= Lower limit; s= Primary facility result; and x= Secondary facility results.

- The remaining hematology, serum chemistry, and urinalysis test results are considered to have a non-normal distribution (Chuang-Stein, 1992) and the following formula will be used (Karvanen J., 2003):

$$s = \frac{x U_s}{U_x}$$

Prior to applying these formulae, if required, units will be adjusted.

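### The graded laboratory and vital-sign table in protocol 7.6.1 counts only newly abnormal values, so worsening from an already graded baseline is left out of its numerator

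*Protocol*

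**What the plan says.** Protocol 7.6.1 sets two conditions for the graded table. The first is that subjects have "post-vaccination clinical laboratory values or vital sign values recorded as newly abnormal following study vaccination". The second is a grade threshold: values meeting the mild "criteria (Grade 1) or above as specified in the Toxicity Table (Appendix E) will be tabulated at each post-vaccination time point and overall". *Newly abnormal* is not defined, and no clause covers a value that was abnormal before dosing and then worsened. Under protocol 7.6, percentages are taken over all subjects in the safety population.

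Elsewhere the protocol works with grade increases. Section 3.6.3.5 begins its reporting rule with "If the laboratory value is abnormal and has increased in toxicity grade" from baseline and concludes that "it must be reported as an adverse event and repeated promptly to demonstrate resolution". Section 5.3 includes among adverse events "adverse changes from baseline that represent increases in toxicity grade according to the Toxicity Table". The last sentence of the same paragraph in 7.6.1 adds: "Clinical laboratory and vital sign abnormalities will also be reported as adverse events and will be included in the summary of adverse events".

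SAP 9.3 plans a laboratory shift table: "The shift tables will include normal, low, and high relative to the laboratory reference ranges", or normal/abnormal for categorical tests. SAP 9.4 plans no shift table for vital signs. The text of neither section describes a tabulation by toxicity grade.

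**The concern.** The table is the protocol's only described count of subjects by Appendix E criteria for individual laboratory and vital-sign parameters. On its wording it counts a small move out of the normal range and omits a larger move by a subject who started outside it. The protocol therefore applies one rule to decide what is an adverse event and another to decide what enters this table.

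The case can arise, because the entry criteria allow graded baselines. Comparing safety between the RIG and SYN023 regimens is a secondary objective. For CPK and visually read urine dipstick findings, which protocol 6.1 and 6.2 exempt from the pausing and stopping rules, tabulation carries more of the burden of showing what happened.

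**Working it through.** The plan states no figure for this point, so there is nothing to reproduce. The check applies the written rule to cases that the documents allow.

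**Step 1. Can a subject have a graded value at baseline?** Yes:
- Urine protein: exclusion 5 applies at 2+ or above, or if the investigator judges the urinalysis clinically significant. Appendix E grades trace as 1 and 1+ as 2.
- Liver enzymes: exclusion 3 tolerates a single AST, ALT or ALP above ULN. Appendix E Grade 1 starts at 1.1 x ULN.
- Lymphocytes: exclusion 2 applies its limits "at screening with exception of absolute lymphocyte count".
- CPK: no exclusion criterion names it, and 3.2.2 says chemistry beyond AST, ALT, ALP and creatinine is not part of the criteria as such.
- Blood pressure, pulse and respiratory rate: no numeric entry limit, although Appendix E grades all three. Exclusion 11 still removes clinically relevant disease.

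**Step 2. Apply both rules.** Grades are from Appendix E.

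| Baseline to post-dose | Grade change | 7.6.1 rule | Grade-increase rule | SAP shift table |
|---|---|---|---|---|
| ALT 1.0 to 1.2 x ULN | none to 1 | counted | counted | normal to high |
| ALT 1.2 to 6 x ULN | 1 to 3 | not counted | counted | high to high |
| Urine protein 1+ to 2+ | 2 to 3 | not counted | counted | abnormal to abnormal |
| CPK 1.25–1.5 to 3.1–10 x ULN | 1 to 3 | not counted | counted | high to high |
| Systolic pressure 141–150 to >155 mm Hg | 1 to 3 | not counted | counted | none planned |

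**Step 3. How many subjects are affected?** Let f be the share graded at baseline on a parameter, n = 40 per arm (SAP 3.1), and p1 and p2 the chances of a grade increase in subjects without and with a graded baseline.

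- Expected count, grade-increase rule: n[(1 − f)p1 + f·p2]
- Expected count, 7.6.1 rule: n(1 − f)p1
- Missing: n·f·p2

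The documents do not give f, p1 or p2. Assume f between 5% and 30% and, for illustration only, p1 = p2 = 10%, so that the grade-increase rule expects 40 × 0.10 = 4 subjects (10%).

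| f | Cannot be counted (40 × f) | Expected count under 7.6.1 | Percentage shown |
|---|---|---|---|
| 5% | 2 | 40 × 0.95 × 0.10 = 3.8 | 9.5% |
| 20% | 8 | 40 × 0.80 × 0.10 = 3.2 | 8.0% |
| 30% | 12 | 40 × 0.70 × 0.10 = 2.8 | 7.0% |

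When p1 = p2, the relative undercount equals f. In this illustration it is about one subject per arm or fewer.

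**Step 4. Where else would the worsening appear?**
- Adverse event summaries, by the rules in 3.6.3.5, 5.3 and 7.6.1. There are two limits. Section 5.4 records Grades 3 and 4 together as severe. Unsolicited events are collected to Day 42 (3.6.3.6, SAP 9.2.2), while Table 3.1-1 repeats chemistry, CBC, coagulation, urinalysis and vital signs on Day 112.
- Listings of all laboratory and vital-sign results (SAP 9.3, 9.4).
- Descriptive statistics with minimum and maximum, for values and for change from baseline (protocol 7.6.2, SAP 9.3, 9.4), and frequencies of each urinalysis result (SAP 9.3).

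Of these, only the adverse event summaries give a count by severity. None shows baseline grade against worst grade by treatment.

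**The case against.** The strongest reply is that the main safety analysis already captures these cases. Adverse events are the primary safety variable in 7.6.1, a laboratory grade increase must be reported as one, and each subject is shown at the greatest severity. An ALT going from 1.2 to 6 x ULN would also appear in the listing, and in an arm of 40 would probably set or approach the maximum change. This stands, and it limits the point to one supportive table.

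The Day 42 limit is also narrow. Among scheduled laboratory and vital-sign visits only Day 112 falls after it, serious events are collected to Day 112, and 3.6.3.5 states no time limit. What remains is a non-serious worsening first seen on Day 112, which SAP 9.2.2 places outside the unsolicited window.

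A programmer might read *newly abnormal* as newly at a higher grade. The text does not say so, and 5.3 names new events and worsening separately where it means both. The ambiguity is itself a reason to define the term.

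Three stronger readings are tempting and are not supported:
- *The worsening is counted nowhere, or can reach only the adverse event tables.* Step 4 shows otherwise.
- *The RIG versus SYN023 comparison is biased.* Randomisation balances abnormal baselines in expectation, and nothing in the documents shows a direction.
- *The table loses its ability to rule out rare events.* With 80 SYN023 recipients and an assumed 10% to 30% graded at baseline, 72 to 56 could be counted. The zero-event bound 1 − 0.05^(1/n) then moves from 3.7% to between 4.1% and 5.2%. The arithmetic is right, but no such bound is planned for this table and SAP 9 excludes inference on safety data.

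**Conclusion.** The point holds for the graded table in 7.6.1. Its rule omits worsening from a graded baseline, keeps those subjects in the denominator, and disagrees with the grade-increase rule in 3.6.3.5 and 5.3. The SAP shift table does not recover them.

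The size is modest. Under an assumed 5% to 30% graded at baseline, 2 to 12 of 40 subjects per arm cannot be counted on a given parameter, and the number of worsenings actually missed is a fraction of those. The true prevalence is unknown from the documents. The residual gap in graded reporting is narrow: Grades 3 and 4 are not separated, and non-serious Day 112 values may be missed. The conclusion rests on the plain meaning of *newly abnormal*. It holds whether the table is produced from the protocol or taken into the SAP unchanged.

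**What to change.** In 7.6.1, or through the SAP as protocol 7.8.2 allows, replace the newly-abnormal condition with: subjects whose post-dose Appendix E grade is higher than their pre-Study Drug grade, at each time point and overall. Add to SAP 9.3 and 9.4 a table of baseline grade by worst post-dose grade, per parameter and treatment, with Grades 3 and 4 kept separate and Day 112 included.

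Limit this to parameters both graded in Appendix E and scheduled in Table 3.1-1:
- **Chemistry:** sodium, potassium, calcium, BUN, creatinine, CPK, ALP, AST, ALT and bilirubin.
- **Haematology and coagulation:** the graded blood count items, INR and PTT.
- **Urine:** protein and glucose, and microscopic blood where examined.
- **Vital signs:** temperature, pulse, blood pressure and respiratory rate.

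Appendix E also grades serum glucose, magnesium, phosphorus, albumin, total protein, cholesterol, amylase/lipase and fibrinogen, which are not scheduled. For some parameters Grade 4 is defined by hospital care or intervention rather than a value, so the shell should say whether such grades come from the adverse event record.

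The cost is one revised sentence and a table shell, with no new data. The counts become slightly less favourable. Editing the protocol itself needs sponsor and IRB/IEC approval (section 12). The SAP route needs sponsor approval (SAP 1).

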### **7.6.2 Clinical Laboratory and Vital Sign Parameters**

For each clinical laboratory parameter and vital sign parameter prespecified in the protocol, summary statistics for continuous parameters will be presented by treatment regimen for all pre- and post-Study Drug assessments and for change from pre-Study Drug to post-Study Drug assessments.

Statistical methods: Analysis of Safety

Safety analyses will be performed using the Safety Population, as defined in Section 7.1. Count and percent summaries will be presented by treatment group for all subjects.

Descriptive statistics (number of subjects, mean, standard deviation, percent coefficient of variation, median, minimum, and maximum) will be used to summarize all safety and laboratory data.

### **7.7 Sample Size Considerations**

The sample size for this Phase 2 study was selected based on requirement to consider noninferiority of the efficacy parameter, RVNA. The power analysis was performed in SAS 9.2 using the power procedure for noninferiority testing under the assumption of the sample size of 40 per group and likely margin corresponding to SYN023 being no less than 10% lower than RIG. Based on earlier studies, the mean RVNA for 0.3 mg/kg SYN023 of 20 with CV of 15-25% are reasonable. For assumed underlying differences of 0 to 1 IU/mL, there is over 80% to conclude non-inferiority of RVNA level at a specified time point. The sample size of 40 per treatment group should be sufficient to address the efficacy objectives of the study.

The assumptions that a difference of 2 or less is considered unimportant (the approximate mean value for 0.3mg/kg SYN023 of 20 was used), with the range in mean difference from -1 to 1, standard deviation of 3 and power of 0.8, the required sample size of 29 is needed to declare that the new treatment (SYN023) is not more tolerably inferior to the previous treatment (RIG). Also, the power analysis was performed for the sample size of 40, standard deviation 3 and the mean difference of 2. This resulted in the power of 0.838. The above results from the sample size and power analysis showed that the sample size of 40 should be sufficiently powered for this study.

Also, a power analysis for non-inferiority of the AUCs was performed using “PowerTOST”, an R CRAN package run under Rstudio version 0.99.491. Under the assumption of a lower non-inferiority bound of 0.9 (corresponding to SYN023 being no less than 10% lower than RIG), the selected sample size of 40 per group would provide over 80% power assuming a CV of 10-20%.

If no SAEs are observed among subjects in each dose group and the 40 subjects in the 3 dose groups combined, the one-sided exact upper 95% confidence bounds on the rate of SAE occurrence will be 45% and 18%, respectively.

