#### **1.5 Clinical Experience with SYN023**

SYN023 administration exhibited an acceptable safety profile in protocol SYN023-001. There were no SAEs or acute allergic reactions and local toxicity was mild. SYN023 antibody concentrations are pending for Study SYN023-001, however RVNA determinations are final. All five subjects in each dose group of protocol SYN023-100 lacked RVNA prior to SYN023 injection and exhibited measurable RVNA after administration thus, it is reasonable to conclude that the RVNA was the result of SYN023 antibody injection. If this is true then the two higher doses of 1.0 mg/kg and 3.0 mg/kg exceeded rabies virus neutralizing activity for 84 days and the mean level of the lowest dose of SYN023 tested in Protocol SYN023-001 (0.3 mg/kg) exceeded rabies virus neutralizing activity ( $\geq 0.5$  IU/mL) by over five-fold in the serum for at least 28 days (Table 1.5-1). The descriptive statistics including mean, standard error and 95% confidence intervals were calculated by SAS 9.4 (Cary, NC, USA) and figure 1.5-1 was generated using Graphpad Prism 5.0 (San Diego, CA, USA)

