### Criteria for Pharmacodynamic Similarity Acceptance

Rabies Virus Neutralizing Activity plotted against time will be created. Pharmacodynamic parameters for SYN023 mAb will be estimated using non-compartmental analysis. Cmax, Tmax, AUC0-last, AUC0-inf will be calculated. For the comparison of RIG to SYN023 with RVi and RVa vaccines: The 90% confidence intervals for the ratio of geometric means (RIG/SYN023) must be 80% to 125%. An ANOVA of the ln-transformed AUC0-inf will be run to determine the 90% confidence interval on the difference between treatments. The confidence interval limits derived on the log scale will be back-transformed to the raw AUC scale for comparison to the acceptance criteria.

To investigate any interference of SYN023 to the immune response generated by the vaccine, a non-inferiority test of the AUC14-last between RIG and SYN023 for each vaccine can be performed. The one-sided 90% confidence interval derived on the log transformed AUC from an ANOVA would be compared to the lower acceptance criterion of 80%.

Additionally, a non-inferiority test of the level of RVNA between RIG and SYN023 for each vaccine at selected time points, such as 14 or 28 days, can be performed using a Wilcoxon rank sum approach with a non-inferiority of 10% of the level associated with RIG. Pharmacodynamic efficacy will be defined as RVNA measured above 0.5 IU/mL with RVi and RVa for the duration of the trial and no more than 10% lower for SYN023 compared to RIG at any time point through Study Day 35.

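### Protocol 7.7 attributes a mean RVNA of 20 to 0.3 mg/kg SYN023, but the protocol's own Phase 1 means at that dose are 1.82-4.44 IU/mL on Days 1-35, so the 2 IU/mL planning margin is not a 10% margin on Days 1-7

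*Protocol*

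**What the plan says.** Protocol section 7.7 bases the time-point sample size on non-inferiority of RVNA, with a "likely margin corresponding to SYN023 being no less than 10% lower than RIG". Its inputs are a mean and a CV: "Based on earlier studies, the mean RVNA for 0.3 mg/kg SYN023 of 20 with CV of 15-25% are reasonable". No unit stands beside the 20, but the next sentence works in IU/mL and claims more than 80% power for true differences of 0 to 1 IU/mL. The second paragraph turns the relative margin into an absolute one: "The assumptions that a difference of 2 or less is considered unimportant (the approximate mean value for 0.3mg/kg SYN023 of 20 was used"). It continues, "with the range in mean difference from -1 to 1, standard deviation of 3 and power of 0.8, the required sample size of 29 is", so that 29 is the number required, and adds that "the power analysis was performed for the sample size of 40, standard deviation 3 and the mean difference of 2", giving power 0.838.

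Section 7.3 sets the optional time-point test at "a non-inferiority of 10% of the level associated with RIG". Sections 2.2 and 7.3 apply the 10% limit against RIG to every time point through Day 35.

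Section 1.5 reports the Phase 1 study, with five subjects per dose, and attributes the measured RVNA to the SYN023 injection. At 0.3 mg/kg, Table 1.5-1 gives means of 2.70, 3.68, 4.44, 3.78, 2.82 and 1.82 IU/mL on Days 1, 3, 7, 14, 28 and 35. The same section says that vaccine-induced RVNA is unlikely from Day 0 through Day 7.

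**The concern.** The planning mean is credited to earlier studies of this dose, yet the one such study in the documents never comes near it. Even at 1.0 mg/kg the highest mean in Table 1.5-1 is 17.00. The 2 IU/mL margin is 10% only of 20. At the levels seen in Phase 1, both the margin and the assumed true differences of up to 1 IU/mL are far larger shares of the mean than the 10% the protocol intends.

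What is at stake is whether the sample-size rationale can be trusted. A reader of a borderline result would go back to section 7.7 and its conclusion that 40 per group is sufficient. That reader would find an unsourced mean, an absolute margin that does not match the stated criterion at the early visits, and a power claim covering the whole CV range.

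**Working it through.** **1. Reproducing the plan's figures.** Section 7.7 states no alpha. For a two-sample t test with n per group,

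ncp = (margin − true deficit) / (SD × √(2/n)), and power = P[noncentral t with 2n − 2 df exceeds the critical value].

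- Margin 2, SD 3, zero difference, one-sided 5%, power 0.80: n = 29. This matches.
- n = 40, SD 3, difference 2: ncp = 2 / (3 × √(2/40)) = 2 / 0.671 = 2.98. Power is 0.838 at two-sided 5% (equivalently one-sided 2.5% with zero true difference), which matches. At one-sided 5% it is 0.905.

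Both figures reproduce from their inputs, though at different alphas. The problem lies in the inputs.

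**2. The mean of 20 against Table 1.5-1 (0.3 mg/kg).** The ratio is 20/4.44 = 4.5 at the peak and 20/1.82 = 11.0 on Day 35.

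**3. The absolute inputs where the comparison is fair, Days 1-7.**

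| Day | Phase 1 mean (IU/mL) | 2 / mean | 1 / mean | 10% of mean (IU/mL) |
|---|---|---|---|---|
| 1 | 2.70 | 74% | 37% | 0.27 |
| 3 | 3.68 | 54% | 27% | 0.37 |
| 7 | 4.44 | 45% | 23% | 0.44 |

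The planning SD of 3 would likewise be 3/4.44 = 68% to 3/2.70 = 111% of these means, not 15%.

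**4. Does the mean drive the sample size?** Write the margin as 0.10 × mean and the SD as CV × mean. At zero difference and n = 40,

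ncp = 0.10 × mean / (CV × mean × √(2/40)) = 0.10 / (0.2236 × CV).

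The mean cancels. At one-sided 5%:

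| CV | ncp | Power, 40 per group |
|---|---|---|
| 15% | 2.98 | 90% |
| 20% | 2.24 | 72% |
| 25% | 1.79 | 55% |

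These hold at a mean of 20 or of 4.44. The claim of over 80% therefore fails within the plan's own 15-25% CV range even with no true difference. At mean 20, SD 3 and a true deficit of 1 IU/mL, power is 43%.

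**5. Can Table 1.5-1 settle the CV?** Its ± is not labelled. Section 1.5 says "The descriptive statistics including mean, standard error and 95% confidence intervals were calculated by SAS 9.4" and does not mention a standard deviation. With n = 5, the CVs on Days 1, 3, 7, 14 and 28 are:

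- ± read as SD (±/mean): 15.9, 15.2, 24.5, 10.8, 21.6%.
- ± read as SE (multiply by √5): 35.6, 34.0, 54.9, 24.3, 48.4%.
- ± read as a 95% CI half-width (multiply by √5/2.776): 12.8, 12.3, 19.8, 8.7, 17.4%.

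Power for a 10% margin on those days, under the conditions of step 4, runs 56-99% under the first reading, 20-57% under the second, and 73% to over 99% under the third. The table neither confirms nor contradicts a CV of 15-25%.

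**The case against.** The strongest reply is that 20 was meant as total RVNA once vaccine has taken effect. Every subject receives five vaccine doses, section 1.1 expects virtually all vaccinees to have adequate activity by Day 14, and section 7.3 names Days 14 and 28 as examples for the time-point test. This stands in part. A level near 20 may be plausible at later visits, so Table 1.5-1 should not be held against Days 14-35. But section 7.7 attributes the figure to SYN023 and to earlier studies, names no time point, and gives no level or SD for SYN023 with vaccine. The 10% criterion also covers Days 1-7.

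A second reply is that nothing in the trial is judged against 2 IU/mL. That is right. Section 7.3 uses a percentage of the RIG level, SAP section 10.4.1 requires a ratio interval within 80.00-125.00% for AUEC0-t, and SAP section 10.4.2 reports ratios. A reader might infer that the trial would accept a 45-110% deficit as unimportant; the documents do not support that.

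Third, section 7.7 contains a separate AUC power calculation with a 0.9 bound and CV of 10-20%. It uses neither the 20 nor the 2, and the SAP's primary parameter is AUEC0-t. The sample size therefore does not rest on the time-point inputs alone.

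Finally, taking the margin from a SYN023 mean when the criterion refers to RIG looks like a choice of the wrong arm. At zero true difference 10% of either mean is the same, so this is a matter of labelling, although no RIG level is stated anywhere.

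**Conclusion.** The point holds as a fault in the planning inputs. The mean of 20 for 0.3 mg/kg SYN023 is unsourced and is 4.5 to 11 times the Day 1-35 means in the protocol's only human data at that dose. On Days 1-7 the 2 IU/mL margin is 45-74% of the Phase 1 means and the 1 IU/mL difference is 23-37%, so neither represents a 10% margin there. This assumes that Phase 1 levels predict the SYN023 arms before vaccine responds, as section 1.5 implies.

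Two further inferences are tempting and not supported. One is that 40 per group is too few because the mean is wrong: with a 10% margin and an SD proportional to the mean, power depends only on the CV. The other is that Table 1.5-1 disproves the 15-25% CV: that turns on an unlabelled ±, and its three readings point in different directions. The power claim does need restating, because over 80% does not hold across the plan's own CV range.

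**What to change.** In protocol section 7.7:

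- Remove the attribution of 20 to 0.3 mg/kg SYN023 from earlier studies, or relabel it as an assumed total RVNA after vaccination at a named time point.
- Replace 2 IU/mL with a SYN023/RIG ratio of 0.90, in line with section 7.3 and the SAP's ratio analyses. The SAP forms its ratios as RIG/SYN023, so the same limit there is 1/0.90 = 111.1%.
- Replace the claim of over 80% time-point power with power over an explicitly assumed CV range, stating alpha: for 40 per group, a 10% margin, zero difference and one-sided 5%, 90% at CV 15%, 72% at 20% and 55% at 25%.

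In section 1.5, say what the ± in Table 1.5-1 is. The CV should not be taken from that table alone, since it describes five unvaccinated subjects.

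The cost is protocol wording and a less favourable stated power. Enrolment and procedures do not change.
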